### **Data Storage and Confidentiality**

During this study, participants will view racially congruent or incongruent Facebook ads and answer survey questions about them. Afterwards, participants will complete a food purchasing task and answer demographic questions. All of the material collected are for research purposes only, and data will be kept in strict confidence. Demographic and survey data will be collected using Qualtrics, a survey software company that hosts the survey data. Qualtrics Enacts several safeguards to protect online data. Qualtrics FedRAMP certified which is one of the highest non-military security programs for security certifications. FedRAMP was initially designed to asses, authorize, and monitor cloud software providers and protect the data housed in federal agencies but has since expanded to protect third-party platforms and systems, like Qualtrics. Finally, our consent and assent form will inform parents and adolescents that although a data breach is possible, it is unlikely. No information will be given to anyone without permission from the subject. The consent and assent forms include the informed consent and assent statements required by New York University School of Medicine for studies Involving Adolescents. This statement guarantees confidentiality and identifies the subject as the owner of the information from the collected data Furthermore, since this is a NIH-sponsored study, we will be issued a Certificate of Confidentiality which prohibits the disclosure of identifiable, sensitive research information to anyone not connected to the research. Confidentiality will also be ensured by use of identification codes. All data will be identified with a randomly generated identification code unique to the subject. B. Database Protection The database will be secured with password protection. The study manager will receive only coded information that is entered into the database under those identification numbers. Electronic communication with outside collaborators will involve only unidentifiable information. Confidentiality During Adverse Event (AE) Reporting we do not anticipate the occurrence of adverse effects because the study is an online survey study where adolescents will view and rate food ads. Still, AE reports and annual summaries will not include subject-or group-identifiable material. Each report will only include the identification code.

All participant responses will be anonymous. For the study, only the PI will have access to identifiable private information and participant data, which will only be used for research purposes. Other members of the research team will have access to identifiable private information for the purposes of recruitment and scheduling or participant data, but not both

Specific study team members will be in charge of ensuring quality of collected data. During data collection, study team members will record themselves to be reviewed by the data management team to ensure adherence to the study protocol across study team members. The data management team will also review uploaded survey responses for completion and address any issues noted by the study team member. Additionally, study team members will be trained to record any anomalies during the participant interactions and/or data collection that could impact the quality of the data collected (e.g. interruptions of the survey, posters at location encouraging healthy eating, the participant mentioning that they are anticipating a big meal following the survey).

The data containing private information will be stored on RedCap . Only authorized study staff will have access to the study data. One RedCap data collection project will be, and a separate project will be used store etc.). This ensures that the personally identifiable information and research data are segregated. Data users on the research team must agree to restrictions against attempting to identify study participants, destruction of the data after completing their analyses, reporting responsibilities, and proper acknowledgement of the data resource. Any computers holding data will be stored in a locked office.

Study records that do not hold PI or PHI will be collected in a binder that will be stored in a locked cabinet in a locked office. The principal investigator and all other study team members will have access to this binder. Study records including consent forms, assent forms, receipt forms, and any other documentation containing PI or PHI will be put in participant packets and stored in a locked cabinet in a locked room. The Principal Investigator and study team members designated to deal with identifiable information will have access to these packets.

Study documents will be retained for the longer of 3 years after close out or 5 years after final reporting/publication. These documents should be retained for a longer period, however, if required by local regulations. No records will be destroyed without the written consent of the sponsor, if applicable. It is the responsibility of the sponsor to inform the investigator when these documents no longer need to be retained.

### **Risk/Benefit Assessment**

The risks associated with this study, if any, are considered to be minimal and are addressed in the protocol and consent form. There may be some discomfort when using an eyetracker, but reports of this are minimal. Further, participants may experience boredom or irritation when completing the online surveys and other tasks embedded within them. Participants and their caregivers will be

informed that an online data breach is possible, though not likely, and that no identifying information will be collected during the study. Exposure to food ads during in-person lab experiments is known to increase consumption of unhealthy foods among children during the 30-60-minute period after ad exposure. During such studies, researchers provide the snacks in order to measure how many calories are consumed in response to food and exposure. This study does not provide snacks to participants, but it's still possible that participants of this study may consume unhealthy foods in response to seeing food ads in our study. Because we are providing a small dose of ad exposure compared to what adolescents view over the course of a week or more, it is unlikely that participating in this study would have longer-term negative influences on participants' diets. To inform adolescents of the possibility that viewing food ads may cause them to eat more calories after the study than they would have otherwise, we will also describe in an online debriefing statement that in-person lab studies involving food ad exposure have shown that children eat more unhealthy snacks in response to seeing food ads compared to non-food ads. The debriefing form will also state that it is possible that participants will experience a desire to consume more food during the 30–60 minutes after the study and should aim to select healthy options such as water, whole fruit, or nuts. The measures taken to reduce any associated risks will be protecting participant information. The study statistician, PI, and Independent Monitor will review adverse event rates monthly. Any Adverse event will be reported to the NYU IRB and NIH.

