### Subject Identification, Recruitment and Consent/Assent

#### **Process of Consent**

#### Aims 1–2

Informed Consent: Electronically signed informed consent will be obtained from each parent/primary caregiver and an electronically signed assent form will be obtained from each subject at entry into the study. Informed Consent is obtained by the following process:

1.Dynata, the online survey company who will recruit participants, will send a consent form to a primary caregiver.

2.Once the caregiver reviews the form and consents their adolescent's participation, Dynata will email the adolescent with the assent form and survey.

3.After reviewing the study and agreeing to participate, the adolescent will sign the assent form and begin the survey

Informed consent/assent and debriefing procedures: Parents whose adolescents are eligible for the survey will receive a link to the informed consent form; if they sign it, then the adolescent will receive a link to an assent form. This will be done through Dynata, a survey firm that maintains an online participant panel of adolescents and adults in the U.S. We have recruited thousands of adolescents through Dynata for pilot research and published studies. Dynata conducts a rigorous, three-step

<sup>35 VanEpps EM, Roberto CA. The Influence of Sugar-Sweetened Beverage Warnings: A Randomized Trial of Adolescents' Choices and Beliefs. *Am J Prev Med*. 2016;51(5):664-672.

recruitment process. First, randomly selected participants who are already members of Dynata's panels are combined with a pool of potential participants who are joining Dynata for the first time after responding to online recruitment materials. Participants will be told in the assent form that researchers are interested in learning about their opinions of social media and consumer brands. This minor deception (i.e., they will not be told the study is about food choices until the end) is commonly used with children in food and research and has been approved by the IRB at NYUGSoM for our previous studies (s19-01102 Ethnically Diverse Study and s15-00879 NYU Media Project).

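### The planned assurance that no identifying information is collected contradicts the protocol's own consent and record-keeping procedures

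*Combined protocol and SAP*

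**What the plan says.** The Risk/Benefit Assessment section plans to tell adolescents and caregivers two things: an online breach could occur but is improbable, and "no identifying information will be collected during the study". Later in the same section it adds: "The measures taken to reduce any associated risks will be protecting participant information".

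Other sections describe what is collected and kept:

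- **Process of Consent, Aims 1–2:** "Electronically signed informed consent will be obtained from each parent/primary caregiver and an electronically signed assent form will be obtained from each subject". The survey firm sends the caregiver the consent form and then emails the adolescent.
- **Process of Consent, Aim 3:** the caregiver signs a form, which is to set out how personal information is used and how identifiers are removed.
- **Data Storage and Confidentiality, paper records:** "consent forms, assent forms, receipt forms, and any other documentation containing PI or PHI will be put in participant packets", held in a locked cabinet.
- **Data Storage and Confidentiality, access:** "only the PI will have access to identifiable private information and participant data". Other team members may have one or the other, but not both.
- **Data Storage and Confidentiality, nature of the data:** "All participant responses will be anonymous". Earlier in that section, all data are said to carry a randomly generated code unique to each subject.

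**The concern.** The sentence in Risk/Benefit Assessment describes what families will be told, so it is more than an internal note. It is joined to the warning about a data breach. A parent weighing that warning would reasonably conclude that a breach could expose nothing that identifies their child. If signed forms and other identifiable records exist, that conclusion is wrong.

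The participants are minors, and the Inclusion Criteria section says they complete an eating-disorder screen at the end of the study. The protocol also withholds the study's focus on food choices until debriefing, as a declared and limited deception. Its other statements to families therefore need to be accurate. What is at stake is participant protection and the clarity of consent, not the calorie comparisons.

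**Working it through.** No arithmetic bears on whether the statements agree, and the plan gives no figure to reproduce. The check sets the statements side by side.

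1. **Does the study collect identifying information?** Risk/Benefit Assessment says it does not. Process of Consent requires electronic signatures from caregiver and adolescent in Aims 1–2 and a caregiver signature in Aim 3. Data Storage and Confidentiality gives some staff identifiable information for recruitment and scheduling, says that personally identifiable information is segregated from research data, and files forms that contain it. A plan to remove identifiers (Aim 3) presupposes that they were collected. These statements cannot all be true.

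2. **Is the assurance limited to the survey dataset?** Its wording covers the whole study. The same section discusses eye-tracker discomfort, which arises only in Aim 3, so the section is not confined to the online surveys.

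3. **Are the responses anonymous?** Data Storage and Confidentiality assigns a code unique to each subject and gives the PI access to both identifiers and participant data. It also relies on a Certificate of Confidentiality, which protects identifiable research information. Those features describe coded, confidential data. The anonymity statement does not fit them.

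4. **Do the two access sentences conflict?** No. Read together, the PI alone may hold both identifiers and data, and every other team member holds at most one. They need no correction, though they do confirm that identifiers exist.

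5. **What are families told elsewhere?** Data Storage and Confidentiality says the consent and assent form will describe a breach as possible but unlikely. It does not repeat the assurance about identifiers. The Aim 3 form is to disclose how personal information is used. Risk/Benefit Assessment does not say in which document, or when, its assurance is given.

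6. **Reach.** Number of Subjects plans 1,252 + 1,300 + 480 = 3,032 adolescents. In Aims 1–2, 1,252 + 1,300 = 2,552 are to provide signed electronic assent, and the protocol describes no specific disclosure about identifiers for them. The 480 in Aim 3 fall under a form described as making that disclosure.

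**The case against.** The best defence is that the assurance was meant only for the online survey. It follows the sentence on survey boredom and speaks of an online breach. The same section says that the study provides no snacks, which fits Aims 1–2 but not Aim 3. In Aims 1–2 the survey firm sends the forms, emails the adolescents and pays them, so the study team may hold few identifiers. Much of the detail on packets, scheduling and on-site conditions reads like in-person work. This is a plausible account of the intent. It does not rescue the sentence, which carries no such limit, and signed forms are part of study entry in Aims 1–2 as well.

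A reader might go further and infer that families consent on a false statement about the study's main risk. The documents do not support that:

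- The consent and assent forms were not available for review. Where the protocol describes their content, the disputed assurance is absent.
- Risk/Benefit Assessment lists several risks and ranks none of them as the main one.
- Protecting information is not the only safeguard. The protocol also plans debriefing advice on eating after the study and resources for participants who report eating-disorder symptoms.
- The problem does not reach all 3,032 participants equally, given the disclosure described for Aim 3.

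**Conclusion.** Wrong as written, and worth correcting. The unqualified assurance in Risk/Benefit Assessment contradicts the signed forms and identifiable records described elsewhere, and the anonymity statement contradicts the coding and access arrangements. If the plan is followed literally, minors and caregivers receive an inaccurate assurance about a risk the protocol names. Aim 3 families could also receive two conflicting messages, one from that assurance and one from their consent form.

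The conclusion rests on the protocol text alone and assumes that the assurance is given as worded. Whether it appears in the consent or assent forms, and whether any family would rely on it when agreeing, cannot be determined from these documents. There is no effect on design, power, estimates or analysis.

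**What to change.** Reconcile Risk/Benefit Assessment, Data Storage and Confidentiality, and the Aim 3 consent section.

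- **Risk/Benefit Assessment:** replace the assurance with a statement for each aim. It should say which identifiers are collected and for what purpose, whether the survey firm or the study team holds them, and that they are stored separately from coded responses. One text for all aims would bring in new errors. For example, Aims 1–2 describe no scheduling, and payment there runs through the survey firm.
- **Data Storage and Confidentiality:** describe responses as coded and confidential instead of anonymous. The two access sentences can stand.
- **Participant-facing texts:** check the consent, assent and debriefing wording against the corrected protocol, and change it where it repeats the old assurance.

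The cost is a wording amendment to the protocol and, if needed, to the forms. No procedure, sample size or analysis changes.

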### Subject Identification, Recruitment and Consent/Assent

#### **Process of Consent**

#### Aims 1–2

Informed Consent: Electronically signed informed consent will be obtained from each parent/primary caregiver and an electronically signed assent form will be obtained from each subject at entry into the study. Informed Consent is obtained by the following process:

1.Dynata, the online survey company who will recruit participants, will send a consent form to a primary caregiver.

2.Once the caregiver reviews the form and consents their adolescent's participation, Dynata will email the adolescent with the assent form and survey.

3.After reviewing the study and agreeing to participate, the adolescent will sign the assent form and begin the survey

Informed consent/assent and debriefing procedures: Parents whose adolescents are eligible for the survey will receive a link to the informed consent form; if they sign it, then the adolescent will receive a link to an assent form. This will be done through Dynata, a survey firm that maintains an online participant panel of adolescents and adults in the U.S. We have recruited thousands of adolescents through Dynata for pilot research and published studies. Dynata conducts a rigorous, three-step

<sup>35 VanEpps EM, Roberto CA. The Influence of Sugar-Sweetened Beverage Warnings: A Randomized Trial of Adolescents' Choices and Beliefs. *Am J Prev Med*. 2016;51(5):664-672.

recruitment process. First, randomly selected participants who are already members of Dynata's panels are combined with a pool of potential participants who are joining Dynata for the first time after responding to online recruitment materials. Participants will be told in the assent form that researchers are interested in learning about their opinions of social media and consumer brands. This minor deception (i.e., they will not be told the study is about food choices until the end) is commonly used with children in food and research and has been approved by the IRB at NYUGSoM for our previous studies (s19-01102 Ethnically Diverse Study and s15-00879 NYU Media Project).

#### Aim 3

In Study 3, the consent form will explain to caregivers the potential risks of the study and what measures have been taken to mitigate these risks. The form will also detail the use of personal information and will explain the removal of identifying information. Caregivers will be asked to sign the consent form, indicating that they understand the risks and preventative measures and that they give consent for the researchers to survey their adolescent and obtain assent.

Our research team will then confirm the adolescent's assent in-person to participate in the study. Before assenting, though, members of our research team will speak with the adolescent about the potential risks, the preventative measures to assess those risks, and the removal of any identifying data. During the study, two researchers will supervise each participant.

#### **Debriefing Procedures**

At the end of the study, participants will view a debriefing statement explaining the study's purpose. We will use a funneled debriefing procedure to ask participants what they believed was the purpose of the study so we can test for moderation of effects as a function of awareness during analyses. We will disclose the purpose of the study, solicit questions, conduct a second assent procedure after disclosing eye-tracking was used and was ethically approved, and provide the same information from the debriefing form in Aim 1 and 2.

To inform adolescents of the possibility that viewing food ads may cause them to eat more calories after the study than they would have otherwise, we will also describe in the online debriefing statement that studies have shown that viewing food ads can increase caloric intake among youth, and they should try to choose healthy options such as water, whole fruit, or nuts if they experience a desire to snack after the study. Dynata will then provide each participant with \$25 in gift cards for participating and \$8 petty cash for the snacks they purchased.

#### Costs to the Subject

Participants will not incur any costs for the first two trials. We will distribute \$35 compensation via gift cards and reimburse travel costs for the third aim .

### Payment for Participation

For Aims 1 and 2- After the food purchasing task, participants will complete demographic questions and then receive \$25 in gift cards for participating and \$8 petty cash for their snack purchases. For Aim 3- Participants will receive \$35 compensation via gift card. We will reimburse participants for any travel costs. To compensate community sites for recruitment assistance, we will provide each site an \$800 honorarium via check.
